8. ACCESS TO SOURCE DOCUMENTS

Access to source documents should be limited during the study. Blinded examiners will have access until the end of the study. All source documents will be made available to Sponsor, any third party with written permission from Sponsor and regulatory agencies.

9. ETHICAL CONSIDERATION

All subjects in this study will receive a standard of oral care. No placebo is involved. This study protocol must be reviewed and approved by the Marquette University IRB prior the study.

10. DATA HANDLING AND RECORD KEEPING

All patient data will be kept in individual booklets with all clinical research forms included. After each visit the patient data booklets will be reviewed by the study coordinator to ensure complete data collection and then kept in a locked file cabinet in the office of the Principle Investigator.

For any subjects screened but found ineligible their screening documents (health history/ charting) will be kept in a screen fail notebook with an explanation as to what the reason was for the screen fail.

11. FINANCING

Each subject will receive reimbursement for expense from the trip to the clinic at the end of baseline and follow-up visits. Reimbursement of \$25 will be given at the baseline and 2-, 4- and 12-week visits in the form of Gift/Gas cards.

12. PROTOCOL AMENDMENT

If it is necessary for the study protocol to be amended, the amendment and/or a new version of the study protocol (Amended Protocol) must be notified to or approved by the MU IRB, and if applicable, also the local regulatory authority, before implementation. Local requirements must be followed.

Sponsor will distribute administrative changes, amendments and new versions of the protocol to the principal investigator.

13. MONITORING

Sponsor will meet with staff members who are involved to review the protocol and ensure that the study will be conducted in accordance with the following:

- Good Clinical Practices (GCPs) Guideline
- The study contract
- Conditions imposed by the IRB
- Any applicable local or federal regulatory requirements

14. STAFF TRAINING

The principal investigator will maintain a record of all individuals involved in the study – dental assistant, oral examiners, and other staff – and ensure appropriate training is given and any new information relevant to the performance of the study is forwarded to involved staff members.

2 WEEKS VISIT – APPROXIMATELY 60 MINUTES

RESEARCH ASSISTANT / STUDY COORDINATOR

CHECKS PATIENT IN

2 WEEK VISIT INFORMATION SHEET

CONFIRMS 7-12 HOUR PLAQUE ACCUMULATION

PATIENT GIVEN RECORD TO CARRY THROUGH THE APPOINTMENT TO EACH STATION

DIRECTS TO 1ST EXAMINERS

1ST EXAMINERS – ORAL CAVITY EXAM, GINGIVAL INDEX, PROBING POCKET DEPTH AND BLEEDING INDEX

2ND EXAMINERS – PLAQUE INDEX

RESEARCH ASSISTANT

CONFIRMS NEXT VISIT (DATE & TIME)

COMPLETES 2 WEEK VISIT EXIT INFORMATION SHEET

RECOVERS PATIENT RECORD FROM PATIENT/ GIVES PATIENT THEIR HONORARIUM

CONFIDENTIAL

4 WEEKS VISIT – APPROXIMATELY 60 MINUTES

RESEARCH ASSISTANT / STUDY COORDINATOR

CHECKS PATIENT IN

4 WEEK VISIT INFORMATION SHEET

CONFIRMS 7-12 HOUR PLAQUE ACCUMULATION

PATIENT GIVEN RECORD TO CARRY THROUGH THE APPOINTMENT TO EACH STATION

DIRECTS TO 1ST EXAMINERS

1ST EXAMINERS – ORAL CAVITY EXAM, GINGIVAL INDEX, PROBING POCKET DEPTH AND BLEEDING INDEX

2ND EXAMINERS – PLAQUE INDEX

RESEARCH ASSISTANT

CONFIRMS NEXT VISIT (DATE & TIME)

COMPLETES 4 WEEK VISIT EXIT INFORMATION SHEET

GIVES NEW TOOTHBRUSH/TOOTHBRUSH HEAD AND/OR TUBE OF TOOTHPASTE PRN

RECOVERS PATIENT RECORD FROM PATIENT/ GIVES PATIENT THEIR HONORARIUM

12 WEEKS VISIT – APPROXIMATELY 60 MINUTES

RESEARCH ASSISTANT / STUDY COORDINATOR

CHECKS PATIENT IN

12 WEEK VISIT INFORMATION SHEET

COLLECTS TOOTHBRUSHES/ CONFIRMS 7-12 HOUR PLAQUE ACCUMULATION

PATIENT GIVEN RECORD TO CARRY THROUGH THE APPOINTMENT TO EACH STATION

DIRECTS TO 1ST EXAMINERS

1ST EXAMINERS – ORAL CAVITY EXAM, GINGIVAL INDEX, PROBING POCKET DEPTH AND BLEEDING INDEX

2ND EXAMINERS – PLAQUE INDEX

RESEARCH ASSISTANT

COMPLETES 12 WEEK VISIT EXIT INFORMATION SHEET

PATIENT EXIT QUESTIONNAIRE

TAKES SUBJECT TO RDH FOR PROPHYLAXIS PRN

RECOVERS PATIENT RECORD FROM PATIENT/ GIVES PATIENT THEIR HONORARIUM

CONFIDENTIAL

PATIENT RECORD

ITEMS INCLUDED IN THE RECORD ARE AS FOLLOWS:

PATIENT APPOINTMENT SCHEDULE

BASELINE VISIT INFORMATION SHEET

BASELINE VISIT – ORAL CAVITY EXAM, GINGIVAL & BLEEDING INDEX/ PD CHARTING

BASELINE VISIT – PLAQUE INDEX PRE- AND POST-BRUSHING

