4.4. Secondary endpoints

The following indices and parameters are secondary endpoints.

- Reduction of BOP and MGI at two-week, four-week visits from the baseline
- Reduction of PPD at 2-week, 4-week and 12-week visits from the baseline
- Reduction in plaque by measuring PI at 2-week, 4-week and 12-week visits as well as after a single use
- Safety of the product: clinical examiners inspect for any hard or soft tissue damage
- Patient reported outcomes from an exit survey and user diary

[figure not shown]
CONFIDENTIAL

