Table 2. Procedure overview during visits

Procedure	Performed by	Visit				
		Screening	Baseline	2-week	4-week	12-week
Plaque accumulation	Subject	X	X	X	X	X
Patient information						
Informed consent form	Study coordinator/staff	X				
Patient demographics	Study coordinator/staff	X				
Medical/dental history	Study coordinator/staff	X				
Oral examination	Blinded examiners					
Oral cavity abrasion exam	Examiners 1 and 2	X	X	X	X	X
Gingival Index (MGI)	Examiners 1 and 2	X	X	X	X	X
Probing Pocket Depth	Examiners 1 and 2	X	X	X	X	X
Bleeding Index	Examiners 1 and 2	X	X	X	X	X
Plaque Index	Examiners 3 and 4	X	X*	X	X	X
Examiner calibration	All examiners	X				X
Others						
Inclusion/exclusion criteria	Study coordinator/staff	X	X			
Prophylaxis	Dental hygienist					X
Randomization	Unblinded staff/study coordinator		X			
Product introduction and instruction	Unblinded staff/study coordinator		X			
Brushing at clinic	Subject		X			
Scheduling future visit	Study coordinator/staff	X	X	X	X	
Collect used brushes	Unblinded staff/study coordinator					X
Exit survey	Subject					X

*Twice

CONFIDENTIAL

Visit 1: Screening and enrollment

Subjects will be asked to report to the clinic with at least 7 but no more than 12 hours of accumulated, non-brushed, undisturbed plaque/debris. Prior to screening, subjects will sign a consent form after having gone over the consent with a member of the study staff and having all questions answered. In this visit, subjects will be asked about dental and medical history related to the admission and exclusion criteria.

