The first follow-up will take place two weeks after the baseline visit. Subjects can schedule the visit for any time between two days before and after the two-week use period (12-16 day range). Clinical examinations will be given to the subjects in the same order as the baseline visit with the exception that no second plaque index will be recorded. All subjects must present with 7 to 12 hours of undisturbed plaque. The oral safety exam will include a thorough examination of the gingiva to look for any signs of gingival trauma, irritation or abrasion. Any subjects who show signs of gingival trauma that appears to be toothbrush related will be exited from the study. The recorded findings will be reported as Adverse Events. In addition, any site in the mouth that shows an increase in probing pocket depth of 2 mm or greater from the baseline measurement will have that particular site treated with subgingival scaling and root planing or whatever the PI deems appropriate therapy. If subjects meet any of the discontinuation criteria, they will be withdrawn from the study.

Visit 4: Four-week follow-up

This visit should take place four weeks after the baseline visit within three days before and after the four week mark (25-31 day range). Subjects will receive full mouth examinations in the same order as the previous visit. Additionally, inspection for signs of gingival trauma and increase in PPD greater than 2 mm from the baseline will be conducted and evaluated. The PI will determine if any subject meets the discontinuation criteria as well as appropriate therapy to treat.

Visit 5: 12-week follow-up

In this visit, subjects will return the products, including manual toothbrush, or brush head, brush handle, and charger. The procedure is similar to the four-week follow-up visit, in which full mouth clinical examination will be carried out as before on each of the subjects. The subjects' disclosed plaque will be evaluated as usual. The examined results will be recorded. Prophylaxis will be carried out as needed.

The used brushes/brush heads will be returned to sponsor at the end of the trial and examined for wear as an additional measure of compliance.

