5.3. Discontinuation criteria

The oral safety exam at the follow-up visits will include a thorough examination of the gingiva to look for any signs of gingival trauma, irritation or abrasion, as well as a periodontal probing. Any subjects who show signs of gingival trauma that appears to be toothbrush related will be exited from the study and the findings reported as Adverse Events. In addition, subjects may be discontinued due to the following reasons.

1. Voluntary discontinuation: subjects are free to discontinue their participation in the study at any time.
2. Safety concerns: the principal investigator may terminate a subject's participation if gingival trauma occurs and appears to be toothbrush related
3. Significant non-compliance to protocol: the principal investigator may terminate a subject's participation if subjects are shown to be non-compliant to the protocol
4. Incorrect enrollment: subjects who did not meet admission/exclusion criteria
5. Subject received any type of dental treatment/care other than those required in the study, for example use of interdental devices, mouthrinses, chewing gum or prophylaxis treatment, without consent of the investigator

Subjects who discontinue should be asked to a follow-up visit to observe any Adverse Events.

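### The exit survey is scheduled only at week 12, so as written this source of the patient-reported secondary endpoint describes completers only

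*Combined protocol and SAP*

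**What the plan says.** Section 4.4 names the patient-reported endpoint and its two sources: "Patient reported outcomes from an exit survey and user diary".

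The survey is placed in two parts of the protocol, and they agree. Table 2 (section 4.5) marks it in the 12-week column and nowhere else. The patient schedule after the references lists "PATIENT EXIT QUESTIONNAIRE" under the 12-week visit; the 2-week and 4-week lists have no such item. Those earlier lists do include an exit information sheet, but the research assistant completes it. The 12-week list carries that sheet as well as the questionnaire, so the two are different items.

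Brush return follows the same timing. Table 2 marks "Collect used brushes" at week 12 only, and the Visit 5 text says "In this visit, subjects will return the products, including manual toothbrush, or brush head, brush handle, and charger". The brushes are then "examined for wear as an additional measure of compliance".

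Early exit is provided for in section 5.3. On injury: "Any subjects who show signs of gingival trauma that appears to be toothbrush related will be exited from the study and the findings reported", with adverse-event reporting named for the purpose. (Item 2 of the list in the same section makes this exit the investigator's option. The two wordings need reconciling, but the survey gap is the same under either.) On choice: "subjects are free to discontinue their participation in the study at any time". For everyone who stops: "Subjects who discontinue should be asked to a follow-up visit to observe any Adverse Events". That sentence mentions no survey, diary or brush.

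The user diary is named in section 4.4 but does not appear in Table 2 or in the patient schedule. Section 7 gives no analysis or missing-data rule for patient-reported outcomes.

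**The concern.** An exit survey is meant to capture what users thought of the brush. A survey given only at the last visit selects on having stayed, and staying may be related to opinion. The subjects with the clearest bad experience, those exited for brush-related trauma, leave before the only scheduled survey.

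Two results could be affected. The level of favourable response in each arm is overstated if leavers are less satisfied than completers. The difference between arms is distorted if the arms lose different numbers of subjects, or lose subjects with different opinions. Without survey answers from leavers, the sponsor could not show afterwards which case applied. The primary endpoint (change in BOP and MGI) and the sample size are not touched.

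**Working it through.** **Inputs from the documents (section 7.1).** 72 enrolled, 36 per arm; 44 needed after drop-outs; drop-out set at 40%.

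**The plan's own figure.** 44 / (1 − 0.40) = 73.3, or 74 for two equal arms. The plan states 72, which is within 2 subjects. Put the other way, 1 − 44/72 = 38.9%. The 40% and the 72 are close enough to use together.

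**Survey coverage as scheduled.**

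- 40% drop-out: 72 × 0.60 = 43.2 surveyed; 72 × 0.40 = 28.8 not surveyed.
- 20% drop-out: 72 × 0.20 = 14.4 not surveyed.
- 10% drop-out: 72 × 0.10 = 7.2 not surveyed.

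**Overstatement within one arm or overall.** Let d be the drop-out proportion, c the percentage of completers who are favourable, and l the percentage of leavers who would have been. The survey shows c. The figure for all randomised subjects is (1 − d) × c + d × l. The overstatement is therefore d × (c − l).

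The documents give neither c nor l. Assume c = 80% and let l run from 50% to 80%:

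| Drop-out | l = 50% | l = 65% | l = 80% |
|---|---|---|---|
| 40% | 0.40 × 30 = 12 points | 0.40 × 15 = 6 points | 0 |
| 20% | 0.20 × 30 = 6 points | 0.20 × 15 = 3 points | 0 |
| 10% | 0.10 × 30 = 3 points | 0.10 × 15 = 1.5 points | 0 |

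At 40% and l = 50%, the survey would show 80% where all randomised subjects would give 0.60 × 80 + 0.40 × 50 = 68%.

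**Distortion of the arm comparison.** The error in the difference is the overstatement in one arm minus that in the other. All cases below keep c = 80% in both arms.

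- Equal drop-out and equal leaver opinion: 0.
- Drop-out 50% and 30% (assumed), l = 50% in both: 0.50 × 30 − 0.30 × 30 = 15 − 9 = 6 points. With l from 60% down to 20%, it is 0.20 × 20 = 4 to 0.20 × 60 = 12 points.
- Drop-out 40% in both, l = 50% in one arm and 80% in the other (assumed): 0.40 × 30 − 0.40 × 0 = 12 points.

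**The case against.** The strongest reply is that silence is not exclusion. Table 2 has no column for early discontinuation, so a missing mark there does not bar a leaver from the survey, and section 5.3 does not say that adverse events are all that may be recorded at the follow-up visit. This stands as far as it goes: staff could give the survey. But nothing tells them to, and the steps that are written down produce answers from completers only.

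Several stronger readings are tempting, and the documents do not support them.

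- *That the whole endpoint omits everyone who stopped early, because the diary yields nothing either.* The diary is a second source, and entries made before leaving could count. Its absence from Table 2 and the schedule leaves its handling unspecified, for completers and leavers alike. The list of patient-record forms and part of Schematic 1 are also incomplete in the available text, so any statement of absence is limited to Table 2, the visit descriptions and the visible schedule.
- *That injured subjects disappear from the data.* They do not. Brush-related trauma is reported as an adverse event, section 6.4 records onset, action, outcome and relationship to the device, and tissue safety is its own secondary endpoint. What is missing is the subject's own rating of the brush.
- *That brush wear is lost for leavers.* The Visit 2 text tells subjects to bring their brush to later exam sessions, so someone exited at week 2 or 4 should have it there. Collection at that point is simply not written down. Wear is also a compliance measure and not part of the patient-reported endpoint.
- *That the survey results are bound to be too favourable.* Section 7.1 attributes drop-out to the trial's duration and number of visits, which is burden and not dislike of the brush. If leavers think as completers do, the bias is zero.

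It is also fair to say that no survey items are given in the available text and no between-arm analysis of the survey is specified, so the comparison at risk is one the sponsor may choose to report, not a planned test.

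**Conclusion.** The point holds for the exit survey. Its only scheduled administration is at week 12, while the plan removes or releases subjects before then and asks them back for adverse events alone. As written, the survey describes about 43 of 72 subjects at the planning drop-out rate and leaves about 29 out.

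The direction and size of any bias are conditional. With 80% of completers favourable and 50% to 80% of leavers favourable, both assumed, the overstatement is 0 to 12 points at 40% drop-out and 0 to 3 points at 10%. The arm comparison is unaffected if drop-out and the completer-leaver gap in opinion are the same in both arms; otherwise it can be distorted by amounts of similar order. The 40% is a planning allowance, and actual drop-out may be lower.

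This is a minor matter of design for a secondary endpoint. It is worth correcting because the correction is cheap before the study and impossible after it.

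**What to change.** In section 5.3 and Table 2, state that a subject who discontinues completes the exit survey, and hands in the brush and any diary, at the visit where discontinuation occurs or at the follow-up visit already requested. Add an early-discontinuation column to Table 2 so that the step is visible to staff.

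In section 7, state that survey results are reported by arm with early leavers included, alongside time on brush and the number not surveyed in each arm. Some leavers will attend neither visit. The documents do not say how many, so that count matters.

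As a separate clarification, add issue and return of the user diary to Table 2.

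The cost is a few lines of protocol text and a few minutes at a visit the plan already asks for. The drawback is that answers will reflect different lengths of use, which is why time on brush should be shown beside them. The primary analysis and the sample size do not change.

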2 WEEK VISIT INFORMATION SHEET

2 WEEK VISIT – ORAL CAVITY EXAM, GINGIVAL & BLEEDING INDEX/ PD CHARTING

2 WEEK VISIT – PLAQUE INDEX

4 WEEK VISIT INFORMATION SHEET

4 WEEK VISIT – ORAL CAVITY EXAM, GINGIVAL & BLEEDING INDEX/ PD CHARTING

4 WEEK VISIT – PLAQUE INDEX

12 WEEK VISIT INFORMATION SHEET

Have you had regular dental check-ups? Yes No Date of last check-up: _____

Dietary Profile: Do you eat or drink between meals? Yes No

Does your diet include any of the following:

Chewing gum	Yes	No	cookies/cakes/pastries	Yes	No
Candy bars	Yes	No	sugar in coffee or tea	Yes	No
Candy	Yes	No	breath mints/cough drops	Yes	No

Oral Hygiene Status – How often do you brush? _____ Type of toothpaste? _____

Type of brush? Power/manual Hard /soft bristle? How often do you change the brush: _____

Do you use dental floss? Yes No If Yes, how often? Frequent (daily)

Sporadic (weekly)

Infrequent (monthly or less)

What is your major dental concern? _____

To the best of my knowledge, I have answered every question completely and accurately, I will inform study group of any change in my health and/or of medication.

Patient's signature: _____

Reviewed by: _____

Date: _____
